8 INVESTIGATIONAL PLAN

Subjects will report to the test site on Visit 1/Day 0 and go through the informed consent process. Eligibility criteria, medical history, concomitant medications, and concurrent products will be reviewed and recorded. Subject will complete the Sensitive Skin Inclusion Questionnaire parts A and B as part of the inclusion/exclusion eligibility criteria. Should they qualify, the subjects will acclimate to ambient room temperature conditions for at least 15 minutes. After acclimation, the PI will perform Investigator Global Acne assessment, and Cutaneous Tolerance scores. Females of child-bearing potential will have a urine pregnancy test to prove that they are currently not pregnant. If the subject qualifies, he/she will be entered into the study.

Protocol Title: A SINGLE-CENTER CLINICAL STUDY TO EVALUATE THE TOLERANCE OF AN ACNE TREATMENT IN SENSITIVE SKIN SUBJECTS WITH MILD TO MODERATE ACNE VULGARIS

Protocol identification: CO-1701-2511-3728-SACT

Date: 9 March 2017 Final Version 1.0

The subjects will receive written and verbal instructions on how to use the device and products as per section 7.5.1 and Appendices I. The subjects will use the products and the device for the first time, on site, under the supervision of a site staff member.

Subsequent visits will be carried out according to section 8.1.

Protocol Title: A SINGLE-CENTER CLINICAL STUDY TO EVALUATE THE TOLERANCE OF AN ACNE TREATMENT IN SENSITIVE SKIN SUBJECTS WITH MILD TO MODERATE ACNE VULGARIS

Protocol identification: CO-1701-2511-3728-SACT

Date: 9 March 2017 Final Version 1.0

Protocol Title: A SINGLE-CENTER CLINICAL STUDY TO EVALUATE THE TOLERANCE OF AN ACNE TREATMENT IN SENSITIVE SKIN SUBJECTS WITH MILD TO MODERATE ACNE VULGARIS

Protocol identification: CO-1701-2511-3728-SACT

Date: 9 March 2017 Final Version 1.0

The Fitzpatrick skin type is based on the skin's unprotected response to the first 30 to 45 minutes of sun exposure after a winter season without sun exposure. The categories of skin types are as follows:

I	White; very fair; red or blonde hair; blue eyes; freckles; Always burns easily; never tans
II	White; fair; red or blonde hair; blue hazel, or green eyes; Always burns easily; tans minimally
III	Cream white; fair with any eye or hair color; very common; Burns moderately; tans gradually
IV	Brown; typical Mediterranean white skin; Burns minimally; always tans well
V	Dark brown; mid-eastern skin types, black hair, olive skin; Rarely burns; tans profusely
VI	Black; black hair, black eyes, black skin; Never burns; deeply pigmented

2. Investigator Global Acne Assessment – Modified Cook's Scale (Visit 1)

The following scale will be used for the global acne assessment (no half-points may be used):

0	Clear	
1	Almost Clear	
2	Mild	
3	Moderate	
4	Severe	

Protocol Title: A SINGLE-CENTER CLINICAL STUDY TO EVALUATE THE TOLERANCE OF AN ACNE TREATMENT IN SENSITIVE SKIN SUBJECTS WITH MILD TO MODERATE ACNE VULGARIS

Protocol identification: CO-1701-2511-3728-SACT

Date: 9 March 2017 Final Version 1.0

5	Very Severe
---	-------------

3. Cutaneous Tolerance Scores (Visit 1, Visit 2 and Visit 3)

Note: For enrollment (see Inclusion Criterion #8), an individual must have a score of 0 or 1.0, not higher, for all tolerance parameters at baseline.

To be evaluated by the Investigator

Erythema

0 = None

1 = Mild

2 = Moderate

3 = Severe

Dryness/Scaling

0 = None

1 = Mild

2 = Moderate

3 = Severe

Edema

0 = None

1 = Mild

2 = Moderate

3 = Severe

To be evaluated by the subject: (No half points to be used)

Burning/Stinging

0 = None

1 = Mild

2 = Moderate

3 = Severe

Itching

0 = None

Protocol Title: A SINGLE-CENTER CLINICAL STUDY TO EVALUATE THE TOLERANCE OF AN ACNE TREATMENT IN SENSITIVE SKIN SUBJECTS WITH MILD TO MODERATE ACNE VULGARIS

Protocol identification: CO-1701-2511-3728-SACT

Date: 9 March 2017 Final Version 1.0

1 = Mild	
2 = Moderate	
3 = Severe	

Tightness/Dry Feeling	
0 = None	
1 = Mild	
2 = Moderate	
3 = Severe	

5.1) Sensitive Skin Inclusion Criteria Questionnaire Parts A and B (Visit 1 only)
(see separate document)

PART A: Sensitive Skin Inclusion Criteria Questionnaire

Subjects must answer either "All of the time" or "Most of the time" to the following question:

Protocol Title: A SINGLE-CENTER CLINICAL STUDY TO EVALUATE THE TOLERANCE OF AN ACNE TREATMENT IN SENSITIVE SKIN SUBJECTS WITH MILD TO MODERATE ACNE VULGARIS

Protocol identification: CO-1701-2511-3728-SACT

Date: 9 March 2017 Final Version 1.0

Do you consider your facial skin to be sensitive?

- None of the time
- Some of the time
- Most of the time
- All of the time

PART B: Sensitive Skin Inclusion Criteria Questionnaire

Subjects must answer "yes" to at least 1 of the following 4 questions.

Question #	Question	Response
1	In the past, have you ever experienced skin irritation (itching, burning, redness, dryness, stinging) when using topical acne treatments?	Yes or No
2	In the past, have you ever stopped using a topical acne treatment due to skin irritation (itching, burning, redness, dryness, stinging)?	Yes or No
3	Have you ever been told by a dermatologist, physician, esthetician or other professional that you have sensitive skin on your face?	Yes or No
4	When purchasing skincare products (facial cleansers, facial moisturizers, makeup, etc.), do you look for products labelled "for sensitive skin" or similar?	Yes or No

Protocol Title: A SINGLE-CENTER CLINICAL STUDY TO EVALUATE THE TOLERANCE OF AN ACNE TREATMENT IN SENSITIVE SKIN SUBJECTS WITH MILD TO MODERATE ACNE VULGARIS

Protocol identification: CO-1701-2511-3728-SACT

Date: 9 March 2017 Final Version 1.0

6) Subject Diaries (Visit 1 through Visit 3)

Subject diaries will be completed at home morning and night to record their product use every day.

8.3 SUBJECT COMPLETION/WITHDRAWAL

8.3.1 Subject Completion

Subjects are considered to have completed the study when all study procedures have been completed as designated by the protocol. Completion should be noted on the Screening and Enrollment log.

8.3.2 Subject Withdrawal

When an individual who has signed the ICD is not enrolled in the study or withdraws/is withdrawn prior to completing the study, the reason is to be documented on the Screening and Enrollment log and will be noted in the final study report.

Reasons for subject withdrawal may include:

- Adverse Event / SAE (must be reported in accordance with the reporting requirements defined in the AE/SAE section).
- Not enrolled (e.g. fails to meet inclusion/exclusion criteria, chooses not to enroll, etc)
- Participant is determined to be ineligible after enrollment
- Subject's choice to withdraw
- Investigator terminated (e.g. noncompliance, etc.)
- Study terminated by sponsor
- Lost to follow-up
- Screen Failure

Protocol Title: A SINGLE-CENTER CLINICAL STUDY TO EVALUATE THE TOLERANCE OF AN ACNE TREATMENT IN SENSITIVE SKIN SUBJECTS WITH MILD TO MODERATE ACNE VULGARIS

Protocol identification: CO-1701-2511-3728-SACT

Date: 9 March 2017 Final Version 1.0

- Death
- Pregnancy
- Other

Subjects may withdraw from the trial at any time at their request, or they may be withdrawn at any time at the discretion of the Sponsor, PI, or designee for safety, behavioral, or administrative reasons. If a subject does not return for a scheduled visit, three (3) documented attempts will be made to contact the subject in order to establish the reason for withdrawal, and the outcome will be documented. The PI or designee should inquire about the reason for withdrawal, request that the subject return for a final visit, if applicable, and follow-up with the subject regarding any unresolved adverse events.

Should a subject withdraw from the trial and also withdraw consent for disclosure of future information, no further evaluations should be performed and no additional data should be collected. The PI and staff may retain and continue to use any data collected before such withdrawal of consent.

In case of withdrawal or dropouts, subjects may be replaced based on overall enrollment numbers and with the approval of the sponsor.

If a subject misses a scheduled visit, but notifies the study site, they will be allowed to re-schedule their missed visit if it is within the (visit window) as specified in Table 1: Schedule of Events. If, it is outside the visit window, they should return for the next study visit. Study staff will need to assess compliance to test product and/or device to ensure missed visit did not result in lack of compliance. This will be documented as a deviation and the sponsor should be notified.

9 STATISTICAL METHODS

Statistical Analysis Population

The cutaneous tolerability evaluations and self-assessment questionnaire data analysis will be performed for subjects in full analysis set (FAS) which is defined as all subjects who use study products and have baseline and at least one post-baseline assessment.

The safety analysis will be based on all subjects who use study products. AE will be listed for safety analysis population.

Demographic Data

Demographic and baseline characteristics [including data from the investigator global acne assessment and the sensitive skin questionnaire at baseline (part A & B)] will be summarized for all subjects who are enrolled in the study. For continuous variables, descriptive summary will include number of subjects, mean, standard deviation, median, minimum and maximum values. For Categorical variables, descript summary will include number and percentage of subjects in each response category.

Cutaneous Tolerance Scores

Protocol Title: A SINGLE-CENTER CLINICAL STUDY TO EVALUATE THE TOLERANCE OF AN ACNE TREATMENT IN SENSITIVE SKIN SUBJECTS WITH MILD TO MODERATE ACNE VULGARIS

Protocol identification: CO-1701-2511-3728-SACT

Date: 9 March 2017 Final Version 1.0

A descriptive statistical summary will be provided for cutaneous tolerance evaluation scores by the investigator and by the subject. The descriptive statistical summary will include the number of observations (N), mean, median, standard deviation (SD), minimum (MIN) and maximum (MAX) at all available visits.

Mean of the change from baseline (defined as post-baseline value minus baseline value) will be estimated at post-baseline time points for applicable parameters. The null hypothesis, that the mean change from baseline is zero, will be tested for applicable parameters using methods described in the Statistical Analysis Plan table.

The following will also be calculated and reported at the applicable post-baseline time point(s):

$$\text{Percent mean change from baseline} = \frac{(\text{visit mean score} - \text{baseline mean score}) \times 100}{\text{baseline mean score}}$$
$$\text{Percent of subjects whose score improved/worsened} = \frac{(\text{number of subjects whose score improved/worsened from baseline}) \times 100}{\text{total number of subjects}}$$

Cutaneous tolerance scores will also be tabulated with count and percent.

Adverse Events

A listing of AEs will be provided, differentiating treatment-emergent AEs.

Statistical Analysis Plan Table

Protocol Title: A SINGLE-CENTER CLINICAL STUDY TO EVALUATE THE TOLERANCE OF AN ACNE TREATMENT IN SENSITIVE SKIN SUBJECTS WITH MILD TO MODERATE ACNE VULGARIS
Protocol identification: CO-1701-2511-3728-SACT
Date: 9 March 2017 Final Version 1.0

All statistical tests will be 2-sided at significance level alpha=0.05. P-values will be reported to 3 decimal places (0.000). No multiple testing corrections will be considered in the study. Statistical analyses are performed using SAS software version 9.4 or later series (SAS Statistical Institute). The statistical results will be sent to the Sponsor along with the raw data in a Microsoft Excel document at the completion of the study.

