PROTOCOL

CO-1701-2511-3728-SACT

PROTOCOL TITLE: A SINGLE-CENTER CLINICAL STUDY TO EVALUATE THE TOLERANCE OF AN ACNE TREATMENT IN SENSITIVE SKIN SUBJECTS WITH MILD TO MODERATE ACNE VULGARIS

PROTOCOL CO-1701-2511-3728-SACT

IDENTIFICATION:

DATE & VERSION: 09 March 2017 Final Version 1.0

SPONSOR: JOHNSON & JOHNSON CONSUMER, INC.

STUDY SITES: Tennessee Clinical Research Center

[name]

PRINCIPAL [name]
INVESTIGATORS
(PIs):

STUDY MANAGER:

STUDY DIRECTOR:

DEPARTMENT
HEAD:

DESIGNATED
PHYSICIAN
REPRESENTATIVE
(DPR):

This study will be performed in compliance with International Conference on Harmonization Guidelines for Good Clinical Practice (E6).

CONFIDENTIAL: The information in this document contains trade secrets and commercial information that are privileged or confidential and may not be disclosed unless such disclosure is required by Federal or State law or regulations. Subject to the foregoing, this information may be disclosed only to those persons involved in the study who have a need to know, but all such persons must be instructed not to further disseminate this information to others. These restrictions on disclosure will apply equally to all future information supplied to you, which is indicated as privileged or confidential.

Protocol Title: A SINGLE-CENTER CLINICAL STUDY TO EVALUATE THE TOLERANCE OF AN ACNE TREATMENT IN SENSITIVE SKIN SUBJECTS WITH MILD TO MODERATE ACNE VULGARIS

Protocol identification: CO-1701-2511-3728-SACT

Date: 9 March 2017 Final Version 1.0

VERSION TRACKING

VERSION	DATE	STATE	REASON FOR CHANGE	DESCRIPTION OF CHANGE
1.0	09MAR2017	Final	N/A	N/A

SYNOPSIS

PROTOCOL IDENTIFICATION	CO-1701-2511-3728-SACT
PROTOCOL TITLE	A SINGLE-CENTER CLINICAL STUDY TO EVALUATE THE TOLERANCE OF AN ACNE TREATMENT IN SENSITIVE SKIN SUBJECTS WITH MILD TO MODERATE ACNE VULGARIS
PRINCIPAL INVESTIGATOR	[name]
STUDY SITE	Tennessee Clinical Research Center [REDACTED]
OBJECTIVE	The objective of this study is to evaluate the tolerance of a light therapy-based acne treatment in subjects with mild to moderate acne and self-reported sensitive skin over a 28-day period.
STUDY DESIGN	This is a single-center, monadic clinical trial to assess the tolerance of the test product on female and male subjects 12-40 years of age with mild to moderate acne vulgaris and sensitive skin. [REDACTED] [REDACTED] Tolerance measures will be signs and symptoms of irritation and adverse events, evaluated by the Investigator and subjects

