4 STUDY DURATION

This study will take place over a 28-day period, with the subjects presenting to the test center for 3 visits. Visits will be at Screening/Baseline (Day 0/Visit 1), Day 14 (Visit 2) and Day 28 (Visit 3).

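### Tolerance scores are summarised only in users with a post-baseline assessment, and no visible summary combines scored worsening with unscored early withdrawals for irritation (cheap improvement, minor)

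*Combined protocol and SAP*

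**What the plan says.** Section 9 sets two analysis populations. Tolerance scores are analysed in the "full analysis set (FAS) which is defined as all subjects who use study products and have baseline and at least one post-baseline assessment". For safety, "The safety analysis will be based on all subjects who use study products", and "AE will be listed for safety analysis population".

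Section 8 gives the scoring times in the entry "Cutaneous Tolerance Scores (Visit 1, Visit 2 and Visit 3". Section 4 places Visit 2 at Day 14 and Visit 3 at Day 28. Section 7.5 has first use of the products in the clinic on Day 0.

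The percent worsened in Section 9 divides the count of subjects whose score worsened by the "total number of subjects", at each applicable post-baseline time point.

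For a subject who withdraws, Section 8.3.2 tells the site to "request that the subject return for a final visit, if applicable". It bars further evaluation if consent to future information is also withdrawn. It allows replacement with sponsor approval and requires the withdrawal reason to appear in the final report.

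The Synopsis treats adverse events as part of tolerance: "Tolerance measures will be signs and symptoms of irritation and adverse events, evaluated by the Investigator and subjects". Section 11.3.2.2 adds that adverse events will be summarised, with treatment-emergent events distinguished, for everyone who signed consent.

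**The concern.** Tolerance is the only objective, and the study is open label with a single arm. Leaving because of irritation is itself a tolerance failure, so a score missing for that reason is missing because of the outcome being measured. There can be up to 14 days of exposure before the first scheduled post-baseline score. The population is also one in which early stopping is plausible: one of the four Part B eligibility questions asks about having previously stopped a topical acne treatment because of irritation, although a yes to any one of the four is enough.

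If such a subject leaves before Day 14 unscored, the score summaries rest on those who stayed. With no control arm, nothing else in the score tables would signal the shift. A reader wanting the proportion of users who did not tolerate the regimen would have to assemble it from the score tables, the adverse event output and the withdrawal reasons.

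**Working it through.** **Planned figure.** The visible text states no expected worsening rate, dropout rate or power calculation, so there is no result to reproduce. Section 6 gives only the numbers: up to 45 enrolled for 40 to complete, an allowance of 5/45 = 11.1% for non-completion from all causes.

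**What happens to the subject.** A user who stops before Day 14 and is not scored has a baseline but no later assessment, and so falls outside the full analysis set.
- If the percent-worsened denominator is the full analysis set, which is the natural reading, the subject is in neither numerator nor denominator.
- If it were all users, the subject would be in the denominator only and would count as not worsened. With 4 worsened this gives 4/45 = 8.9%.

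Neither reading counts the subject as worsened. The means and tests also omit the subject.

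**Illustration of size.** Assumptions: N = 45 product users; x scored subjects worsened on any tolerance parameter; k users stopped for irritation before Day 14 unscored; everyone else has a post-baseline score.
- Rate in the full analysis set = x/(N − k)
- Rate over all users, counting the k withdrawals = (x + k)/N
- Difference = (k/N) × [1 − x/(N − k)]

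| x | k | Full analysis set | All users | Difference (points) |
|---|---|---|---|---|
| 4 | 0 | 4/45 = 8.9% | 4/45 = 8.9% | 0 |
| 4 | 1 | 4/44 = 9.1% | 5/45 = 11.1% | 2.0 |
| 4 | 3 | 4/42 = 9.5% | 7/45 = 15.6% | 6.0 |
| 8 | 1 | 8/44 = 18.2% | 9/45 = 20.0% | 1.8 |
| 8 | 3 | 8/42 = 19.0% | 11/45 = 24.4% | 5.4 |

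Check for x = 4, k = 3: (3/45) × (1 − 4/42) = 0.0667 × 0.9048 = 6.0 points.

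Exact 95% intervals for that row are 2.7% to 22.6% and 6.5% to 29.5%. They overlap widely. The issue is the direction of the point estimate, not a detectable difference.

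**Extreme case.** If all five allowed non-completers left before Day 14, unscored, for irritation, and 4 of the 40 others worsened, the rates would be 4/40 = 10.0% and 9/45 = 20.0%. This is unlikely, because the allowance covers every reason for leaving at any time, and those who leave after a Day 14 score stay in the full analysis set.

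**With replacement.** If 40 enrol, 3 are lost this way and 3 replacements are scored, there are 43 users and a full analysis set of 40: 4/40 = 10.0% against 7/43 = 16.3%.

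**The case against.** The strongest reply is that nothing is lost. Irritation that makes someone stop meets the adverse event definition in Section 11.3.2.1 and must be recorded under Section 11.3.5. Adverse events are a named tolerance measure, are listed for all users and are to be summarised. Withdrawal reasons go in the final report. All of this stands. A reader might infer that early irritation dropouts vanish from the report, but the documents do not support that. The gap is only that no visible summary puts the two components together.

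A reader might also infer that replacement hides the loss, because the score tables could still reach 40. That does not hold either. Demographics are tabulated for all enrolled subjects, so the replacement example would show 43 enrolled against 40 analysed, with reasons given.

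A third tempting reading is that early leavers are never scored. Section 8.3.2 asks for a final visit, and a subject scored there would already qualify for the full analysis set. The visit procedures and schedule of events, which might settle what is done at that visit, are not in the public text. The point is therefore confined to subjects who in fact go unscored, for example because they do not return or withdraw consent to further information.

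It is also fair to say that requiring a post-baseline assessment for score summaries is ordinary practice, since a mean cannot include an absent score. And the rates above are not planned statistics: Section 9 defines percent worsened from a score at a time point, not per subject across parameters. Both objections stand, which is why the planned tables should not change.

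**Conclusion.** The concern holds in a limited form. On the visible text, a user who stops for irritation before Day 14 and is not scored drops out of every score-based summary, and the effect is in the favourable direction. The size is conditional: about 2 percentage points per such loss among 45 users on a subject-level any-parameter rate, and zero if nobody is lost this way. The values of x and k are assumptions, because the documents give no rates.

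A reader might go further and infer that the study's conclusion is biased. The documents cannot show that: the success criteria are redacted, so whether percent worsened drives the conclusion is unknown. The body of the statistical analysis table is also unseen and may already contain such a summary. This is a cheap improvement of minor severity, not the correction of an error.

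**What to change.** Keep the planned full analysis set tables unchanged. Unless the unseen analysis table or success criteria already do so, add to Section 9 one supplementary subject-level row over all subjects who use study products, which is the existing safety population. It should give the number and percent who either
- worsened on any tolerance parameter at any post-baseline assessment, or
- were withdrawn because of irritation or a skin adverse event that is study-related as defined in Section 11.3.2.5.

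Count each subject once, show the withdrawal component separately, and impute no individual scores.

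The cost is a sentence or two of text, one table row and a little more analysis. Part of that work is classifying withdrawals from the adverse event records, because the reasons listed in Section 8.3.2 do not name irritation. The resulting rate may be less favourable than the score tables alone.

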11 MANAGEMENT OF INTERCURRENT EVENTS

11.1 AMENDMENTS TO THE PROTOCOL

Neither the PI nor Sponsor will modify this protocol without obtaining the concurrence of the other. The party initiating a modification will confirm it in writing.

The only circumstance in which an amendment may be initiated prior to IRB approval is where the change is necessary to eliminate apparent immediate hazards to the subjects. In that event, the PI must notify the IRB and Sponsor within 3 working days after the implementation. Amendments must be approved by the Sponsor and IRB/IEC prior to implementation.

Protocol Title: A SINGLE-CENTER CLINICAL STUDY TO EVALUATE THE TOLERANCE OF AN ACNE TREATMENT IN SENSITIVE SKIN SUBJECTS WITH MILD TO MODERATE ACNE VULGARIS

Protocol identification: CO-1701-2511-3728-SACT

Date: 9 March 2017 Final Version 1.0

11.2 PROTOCOL DEVIATIONS

Protocol deviations should be avoided whenever possible. When a protocol deviation occurs, it must be captured in the source documents.

The PI or designee will also contact the Study Manager (see Appendix III) should a Protocol Deviation occur. Contact with the Study Manager will be made as soon as possible in order to discuss the situation and agree on an appropriate action. If it is determined that the subject safety/well-being was affected, the IRB/IEC, if any, will also be notified. The final report will describe the deviation from the protocol and the circumstances requiring it.

